### **6.2.3 Background and Demographic Characteristics**

Demographic data presented will be age, gender, ethnicity/race, years of formal education and Baseline BMI completed for the safety, ITT and PP populations by treatment group and overall.

Body measurements collected at the baseline are weight and height, from which a BMI is calculated. These are summarised for the safety population within Vital Signs section.

Background data (blood type and DAT, HIV1/2, HBV and HCV) will be listed and summarised for the safety population using summary statistics for continuous variables (number of subjects [n], mean, standard deviation [SD], median, minimum and maximum) or by way of group frequencies and percentages for categorical variables, as appropriate.

### **6.2.4 Baseline Disease Characteristics**

Baseline disease characteristics presented will be platelets, LDH, ADAMTS13 activity (subdivided into < 5% and ≥ 5%), ADAMTS13 functional inhibitors (categorised as <0.5 BU/mL, ≥0.5 BU/mL and ≤2 BU/mL, >2 BU/mL, >>2 BU/mL), vWF:Ag levels, initial

---

or recurrent episode (where an episode is considered to be recurrent for subjects with one or more occurrences of MedDRA preferred term “THROMBOTIC THROMOCYTOPENIC PURPURA” at latest, the month preceding the month of first dosing within the Medical History data), PE prior to randomisation (Yes/No) and exploratory markers of disease such as cardiac markers (TnT or TnI, BNP or NT-proBNP) and brain damage markers (NSE, S $\beta$ 100) for ITT and PP populations. ADAMTS13 activity will also be summarised separately for subjects having or not having received one PE prior to randomisation.

Baseline disease characteristic data will be listed and summarised using summary statistics for continuous variables (number of subjects [n], mean, standard deviation [SD], median, minimum and maximum) or by way of group frequencies and percentages for categorical variables, as appropriate.

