8.3.3 Bleeding Events

Clinically relevant bleeding

Incidence of clinically relevant bleeding will be reported. Clinically relevant bleeding is defined as moderate to severe (including life-threatening) bleeding requiring urgent medical and/or surgical intervention.

Modified ITP bleeding score

Bleeding will also be measured using a modified version of the immune thrombocytopenic purpura (ITP) bleeding score. The rationale for using a modified version of the ITP bleeding score is the following. Both the WHO bleeding scale and other bleeding scales used in the frame of cardiac intervention or treatment of venous thromboembolism include bleeding or blood loss requiring transfusion of packed RBC or whole blood as a severity factor. It is common for subjects undergoing PE to need transfusions, even without apparent bleeding. The ITP bleeding score²⁷ does not include transfusion data. It is expected to be more sensitive than the other bleeding scales mentioned above. The modified ITP bleeding score is the sum of the scores for each line (Table 15).

Table 15: Modified ITP bleeding score.

Grade	0	1	2
Skin: petechiae	None	Scattered petechiae	Diffuse petechiae
Skin: ecchymosis	None	1-5 bruises	>5 bruises with size > 2cm
Oral	None	1 blood blister or >5 petechiae or gum bleeding <5 min	Multiple blood blisters or gum bleeding >5 min
Epistaxis	None	Blood when blowing nose or epistaxis <5 min (per episode)	Epistaxis >5 min (per episode)
Ocular	None	Subconjunctival haemorrhage	
Intracranial	None		Haemorrhage
Gastrointestinal	None	Blood when wiping	Blood present on stool
Urinary	None	Dipstick greater than trace	Macroscopic
Gynaecological	Normal period	Spotting outside of normal period	Bleeding greater than spotting outside of normal period, or very heavy period
Pulmonary	None	Haemoptysis	Haemorrhage

Clinically relevant findings that are observed prior to study drug initiation must be recorded on the relevant Medical History source documents page. Abnormalities in local tolerability will be reported via AE reporting throughout the trial. Clinically relevant findings found after study

drug initiation and meeting the definition of an AE (new AE or worsening of previously existing condition) must be recorded on an AE page of the source documents.

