## INTRODUCTION

This is a multicentre, multinational study in which it is anticipated to include 110 adult subjects with acquired thrombotic thrombocytopenic purpura (TTP) from approximately 50 participating sites across approximately 13 countries in Europe, Middle East and Northern America. This population includes symptomatic patients with acute episodes of acquired TTP, requiring treatment with plasma exchange (PE). In a limited number of sites, the trial allows inclusion of adolescent subjects (age 12 - < 18 years) as per EMA PIP (EMEA-001160-PIP01-11).

TTP is a rare and life-threatening disorder of the blood coagulation system, in which accumulation of Ultra large von Willebrand factor (ULvWF) multimers has been implicated, leading to an increased risk of thrombus formation in small blood vessels due to excessive platelet aggregation and is associated with profound thrombocytopenia and erythrocyte fragmentation. The condition is characterized by systemic platelet aggregation in the microcirculation, producing fluctuating ischaemia in many organs. If sustained, this may cause tissue infarction.

ALX-0081 is a bivalent Nanobody, consisting of two identical monovalent building blocks, that target von Willebrand factor (vWF). ALX-0081 is able to interact with vWF in both its active (i.e. functional for interaction with GPIb-IX-V as regular size multimers and as ultra-large multimers) and in its inactive stage (regular size multimers prior to conformational change of A1 domain).

Given the established role of the interaction between vWF and platelet GPIb-IX-V in the pathogenesis of TTP, it is anticipated that ALX-0081 may provide a new option for the treatment of this condition. Therefore, targeting the activity of ULvWF and preventing the interaction with GPIb-IX-V is an attractive concept for treatment and prevention of thrombotic complications in TTP.

The research conducted into TTP over the past three decades has improved the understanding of the pathophysiology of the disease allowing for the potential development of novel agents targeting the underlying disease processes. There are no currently approved therapies for TTP,

---

and although there are newer therapies currently undergoing evaluation, the studies of these potential treatments are at a relatively early stage.

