#### **6.2.8 Plasma Exchange Histories**

PE history (including the one PE within 24 hours prior to randomisation) will be summarised for the ITT population. The number and percentage of subjects who had any pre-study PE history will be summarised by treatment group and overall. The total number of days for pre-study PE per subject will be summarised with descriptive

---

statistics: [n], arithmetic mean, standard deviation [SD], median, range (*i.e.* minimum and maximum values), and 95% confidence intervals for the mean.

PE history will be listed and will include date of TTP diagnosis, whether the subject has a history of PE (Yes or No), date of PE, number of days for PE, and plasma product. An asterisk will be placed indicating the PE which is given within 24 hours prior to randomisation.

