### *Subgroup analyses*

In addition to the KM estimates, the corresponding Cox proportional hazard regression model with baseline disease characteristics (ADAMTS13 activity  $< 5\%$  versus  $\geq 5\%$ , vWF level (continuous), first episode versus recurrent disease (as described in [Section 6.2.4](#)), presence or absence of RICO suppression of  $< 20\%$  throughout treatment period, one PE prior to randomisation or not) will be used to estimate the hazard ratio (HR) and associated 95% CIs for the HR for ALX-0081 and placebo group. This will be represented by means of Forest plots.

The trial was not sized to test for the presence of treatment by subset interactions. Thus true treatment by subset interactions would likely be missed, unless they are substantial. Conversely, should any particular subset of subjects seem to benefit more or less from therapy than the total population, this would not be taken as evidence of a true treatment by subset interaction, given the likelihood that such an observation could be due to chance alone.

Underlying model assumptions will be investigated for the survival analysis using diagnostic statistics and graphical methods, and if necessary, an alternative analysis technique may be used. Any changes in methodology will be documented in the clinical study report (CSR, to be produced by [REDACTED]), including the rationale for use. The proportional hazards assumption will be assessed by graphical display of the log-log survival distribution function versus the log event time for each treatment group.

In order to accommodate tied time-to-event data, the EXACT option within SAS PROC PHREG shall be used. This method assumes that there is a true but unknown ordering for the tied event times, and that the ties are merely the results of imprecise measurements of time.

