### *Sensitivity analyses with regards to primary (and secondary) efficacy endpoints*

Sensitivity analyses comprise the following aspects:

- 1) For efficacy endpoints (EPs) (primary and secondary), analyses performed on per protocol (PP) populations. Details on major deviations are specified in [Appendix II](#).
- 2) Analysis of treatment effect adjusted for the following covariates:
  - a. ADAMTS13 activity at baseline: < 5% vs.  $\geq$  5%,
  - b. von Willebrand Factor (vWF) level (continuous),
  - c. first episode vs. recurrent disease (as described in [Section 6.2.4](#)),
  - d. Ristocetin Cofactor (RICO) suppression < 20% throughout treatment period: yes vs. no,
  - e. absence/presence of one PE session prior to randomisation.

A Cox proportional hazards model is fit to the data, and in addition to treatment, significant (5% significance level; SL) covariates are retained. This will be represented by means of Forest plots for the covariates found to be significant.

- 3) Analysis of non-confirmed and confirmed platelet response (instead of confirmed platelet response only) for the ITT population: see **Table 2**, with changes to
- 4) **Table 1** indicated in **bold green**.
- 5) Assessment of impact (potential bias) of use of rituximab during daily PE: log rank analysis of primary endpoint with subjects censored at time they start using rituximab for the ITT population. Use of rituximab will be determined by using the Concomitant Medications data (both PE related and not PE related) with ATC code “L01XC” (coded term “RITUXIMAB”).

**Table 2: Censoring/event scenarios (for ITT and PP analysis of non-confirmed and confirmed platelet response; changes to Table 1 indicated in bold green)**

Case	Description	Time at risk/ Time to recovery of platelets (days)	Responder	Censored (No = 0; Yes = 1)
1	No event in 30 days of continuous daily PE a	30	No	1
2	At day 30, confirmed recovery of platelets (per protocol)	30	Yes	0
3	At day x b (1 st measurement of platelet recovery), confirmed recovery of platelets, ideal case (per protocol)	x	Yes	0
4	No event occurred and subject is no longer in trial at day x b (including replaced subjects who are dosed)	x	No	1

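### SAP 6.2.4's calendar-month cut can code a first TTP episode as recurrent when its recorded onset falls in the month before first dosing

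*SAP*

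**What the plan says.** SAP 6.2.4 sets the rule in a parenthesis: "where an episode is considered to be recurrent for subjects with one or more occurrences of MedDRA preferred term" "THROMBOTIC THROMOCYTOPENIC PURPURA" dated "at latest, the month preceding the month of first dosing within the Medical History data". All other subjects are initial.

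The flag is used in three places:

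- the baseline disease table (SAP 6.2.4);
- the Cox subgroup model and forest plot of SAP 6.3.1, which lists "first episode versus recurrent disease (as described in" Section 6.2.4);
- item 2 of the sensitivity analyses in SAP 6.3.1, which lists "first episode vs. recurrent disease (as described in" Section 6.2.4) among candidate covariates, each kept only if significant at 5%.

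The primary log-rank test is stratified by prior PE only and does not use the flag.

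Finer information is already planned. SAP 6.2.7 lists onset date, resolution date and ongoing status for each Medical History entry. SAP 6.2.8 says "PE history will be listed and will include date of TTP diagnosis". The rule in 6.2.4 uses only the month. SAP Section 3 and SAP 6.4.1 say how partial birth, medication and adverse event dates are handled; no such rule is given for Medical History.

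**The concern.** Leaving out the dosing month serves a purpose only if the presenting episode may itself sit in Medical History. The month cut then has to separate the presenting episode from earlier ones, and a calendar month does that badly. Whether a subject is first-episode or recurrent comes to depend on where a month boundary falls, not on the disease history.

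The error moves first-episode subjects into the recurrent group. It would misstate the baseline split, blur the first-versus-recurrent comparison in the forest plot and weaken the adjustment in the sensitivity model. Because that model keeps only covariates significant at 5%, a diluted flag could also drop out of it.

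**Working it through.** The plan attaches no figure to this rule, so there is nothing to reproduce first.

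**Inputs**

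- Rule: SAP 6.2.4, as above.
- Planned size: 110 adults (SAP 6.1.4).
- Lag L from recorded onset to first dose: **assumption**, shown at 1, 3 and 7 days. Protocol 8.1.1 puts screening less than 12 hours before the first on-study PE, and Protocol 4.2 allows at most 24 hours between the end of a single earlier PE and the next. Neither limits the time from onset to dose.
- First episodes: **assumption**, 40% to 80% of 110, i.e. 0.40 × 110 = 44 to 0.80 × 110 = 88.
- Entry: **assumption**, every first-episode subject has the presenting episode in Medical History under the TTP term with its onset date. If only some do, the counts fall in proportion.
- Dosing dates spread evenly over the year.

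**Step 1, the boundary.** The shortest gap coded recurrent is 1 day (entry on the 31st, dose on the 1st). The longest gap not coded recurrent is 30 days (entry on the 1st, dose on the 31st of the same month).

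**Step 2, the share miscoded.** An onset L days before dosing falls in an earlier month when the day of the month at dosing is L or less. For L up to 28 that is L dates in each of 12 months, so the share is 12L/365.

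| L (days) | 12L/365 | of 44 | of 88 |
|---|---|---|---|
| 1 | 12/365 = 3.3% | 1.4 | 2.9 |
| 3 | 36/365 = 9.9% | 4.3 | 8.7 |
| 7 | 84/365 = 23.0% | 10.1 | 20.3 |

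**Step 3, direction.** Two dates in one calendar month are at most 30 days apart, so a correctly dated earlier episode with onset more than 30 days before dosing is always captured. The cut does not lose genuine recurrences; the error runs from first to recurrent.

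**Step 4, after the fix.** If an entry with onset 30 days or less before first dosing does not count, the miscoded share at the lags above falls to 0% for fully dated entries. SAP Section 3 places a new event more than 30 days after the last daily PE. A separate earlier episode treated with daily PE therefore has its onset more than 30 days before dosing and is kept.

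**Step 5, the spelling.** The printed term lacks a B (34 characters; the correct spelling has 35). An exact match to a correctly spelt coded term would return no subjects, so everyone would be initial and the covariate constant. This is an alternative to the calendar error: that error arises only once the term is corrected.

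**The case against.** The strongest reply is that the key premise is inferred. No section states that the presenting TTP episode is entered in Medical History. SAP 6.2.7 speaks of pre-study history, and the TTP diagnosis date is listed under PE history in 6.2.8. The protocol sentence nearest to the premise, "Clinically relevant findings that are observed prior to study drug initiation must be recorded on the relevant Medical History source documents page", stands in 8.3.3 on bleeding and does not concern the qualifying diagnosis. If the recorded date is that of diagnosis or admission, a lag near 1 day is plausible and only about 3% are affected. The month cut also works with month-level dates, and it misses no correctly dated genuine recurrence. SAP 6.3.1 already says that apparent subset differences will not be taken as evidence of interaction.

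Most of this stands as a limit on size. It does not rescue the rule. Excluding the dosing month would be pointless if the presenting episode could never appear in Medical History, and 6.2.4 offers no other way to exclude it.

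A reader might infer that every first-episode subject dosed early in a month becomes recurrent. The documents do not support that: the episode must also be entered under the TTP term with an onset in an earlier month, and same-month onsets are coded correctly. A reader might also infer from the misspelling that the recurrent group will be empty. That requires literal programming from the SAP text, and an empty group in the baseline table would expose it. It is a clerical slip.

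**Conclusion.** The rule as stated gives a wrong classification in a definable set of cases. If presenting episodes are recorded in Medical History with their onset dates, about 3%, 10% and 23% of first episodes are coded recurrent at lags of 1, 3 and 7 days: roughly 1-3, 4-9 and 10-20 subjects for 44 to 88 first episodes. The entry practice is inferred from the cut-off itself; the lag and the number of first episodes are assumptions.

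The consequence is confined to the baseline table, one subgroup and one covariate in a sensitivity analysis. It might be tempting to call this a threat to the adjusted primary result or to suspect bias between arms. Neither follows: the covariate-adjusted model is a sensitivity analysis, the primary test does not use the flag, and the flag comes from pre-dose history. Sample size and power do not change. The point is worth correcting because the data needed are already collected and the change is small.

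**What to change.** Before database lock, and without sight of treatment, replace the parenthesis in SAP 6.2.4 with a rule along these lines:

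- **Definition.** Recurrent means at least one TTP episode in Medical History other than the presenting episode.
- **Presenting episode.** Identify it by onset date and ongoing status. For example, an entry does not count if its onset is 30 days or less before first dosing, or if it is ongoing at first dosing with no earlier resolved episode.
- **Partial dates.** A month-only entry for the month before dosing is reviewed case by case against ongoing status. A year-only entry with a recorded resolution before the presenting episode counts as prior. Imputing the latest possible date should be avoided: it would push a year-only earlier episode in the dosing year past the dosing date and turn a true recurrence into an initial episode.
- **Term.** Correct it to THROMBOTIC THROMBOCYTOPENIC PURPURA or match on the MedDRA code.

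Two cautions apply. The diagnosis date in SAP 6.2.8 should not be the anchor unless the sponsor confirms that it refers to the current episode, which the text does not say. The trial's 30 days run from the last daily PE, not from onset, so an earlier entry with onset more than 30 days back but daily PE ending within 30 days belongs in the case review.

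The cost is a short SAP edit, a re-derived flag and a brief masked review of the few records near the boundary.

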#### **6.2.5 Treatment Exposure and Compliance**

Subjects are followed during three separate phases of the study. Treatments only occur during the treatment phase of the study as adjunctive treatment, with treatment times relative to the PE procedures. The study drug consists of 10mg of ALX-0081 or placebo administered during the treatment phase either once or twice daily. Subjects receive a first i.v. bolus of 10mg of ALX-0081 or placebo via push injection within 6 hours but not later than 15 minutes prior to the initiation of PE on study (which can either be the very first PE session, if the subject was randomised prior to the initiation of PE, or the second PE session, if the subject was randomised after one, single PE session). The first PE on study is followed by s.c. administration of 10mg of study drug.

Daily s.c. study drug administration of 10 mg will continue for 30 days after the last PE with a maximum treatment duration of 90 days after the first administration of study drug.

Adolescent subjects will receive weight-based doses according to the same administration schedule as adults.

---

Treatment exposure overall, during daily PE and post daily PE will be summarised by length of exposure in days for the safety population with the details provided in a listing. Compliance is not an issue due to the administration of the study drugs via s.c. methods.

### **6.2.6 Prior and Concomitant Medications and Therapies**

Any prior or concomitant medication taken during the study must be recorded in the CRF. Prior and concomitant medication will be recorded in the CRF separately for medication related to PE versus medication not related to PE.

All medications will be classified using the World Health Organization Drug Dictionary (WHODD) September 2010 Q3 (or later). The Anatomical Therapeutic Chemical (ATC) Classification levels 2 and 4 will be used to list and summarise the data.

Not related to PE: Prior and concomitant medication not related to PE such as methylprednisone, rituximab and other immunosuppressives, will be reported as concomitant medication other than PE-related medication.

Related to PE: Prior and concomitant medication related to PE will be reported as related to the PE. Anticoagulant treatment prescribed as part of the local PE procedure is allowed and considered related to PE. Medication given in response to a PE-related AE (i.e. antibiotic administration due to a central line infection) will be reported in the PE-related concomitant medication section.

The number and percentage of subjects reporting the use of any prior medications by ATC level 2 and ATC level 4 will be summarised for the safety population and for the ITT population by treatment and overall and by relationship to PE.

The number and percentage of subjects reporting the use of any concomitant medications related to PE will be summarised by ATC level 2 and ATC level 4 for the safety population and for the ITT population by treatment and overall.

The number and percentage of subjects reporting the use of any concomitant medications not related to PE will be summarised by ATC level 2 and ATC level 4 for the ITT population by treatment and overall.

The number and percentage of subjects reporting the use of any concomitant medications during follow-up will be summarised by ATC level 2 and ATC level 4 for the ITT population by treatment and overall and by relationship to PE.

Prior and concomitant medications will also be listed and will include reported and ATC terms (levels 2 and 4), indication, dosage, start and stop dates, whether the medication was related to PE and whether the medication was given for an adverse event.

#### **6.2.7 Medical Histories**

Medical history will be summarised for the safety population. The number and percentage of subjects for those who had any pre-study medical history and any pre-study medical history within each body system will be summarised by treatment group and overall. Those conditions that are reported as the underlying cause of TTP will be summarised separately. Subjects reporting more than one condition in a category will be counted only once for that category.

Medical history will be listed and will include reported body system, reported medical history term, date of onset, date of resolution, and ongoing status. An asterisk or an extra Y/N column indicating each line of medical history that is checked off as TTP related equal to Y will be placed.

